**9.2. Study Endpoints - Safety**

Adverse Events:

All subjects who took preparation in any amount will be included in the safety analysis. All adverse events will be summarized based on the principle of treatment emergence. A sign or symptom will be regarded as treatment-emergent if it was present prior to the first dose and subsequently worsened in severity, or was not present prior to the first dose but subsequently appeared.

In order to define treatment emergence for events with missing start or stop dates the following additional criteria will be used:

- if both the onset and resolution dates for a particular event are missing, then the event is considered treatment-emergent;
- if the onset date for an event is missing and the resolution date falls after the initiation of the first dose, then the event is considered treatment-emergent;

- if the onset date for an event falls after the initiation of the first dose and the resolution date is missing or present, then the event is considered treatment-emergent; and
- if the onset date for an event falls before the initiation of the first dose and the stop date is missing or present, then the event is not considered treatment-emergent.

Adverse events will be collected using MedDRA category designations for body system and preferred term. The number and percent of subjects who experienced each adverse event will be presented in a tabular form.

Vitals Signs and Physical Examination:

Vital signs and physical examination data will be summarized with descriptive statistics.

Laboratory Data:

Results of laboratory tests for the change from baseline (Screening) will be summarized with descriptive statistics.

Symptom Questionnaire Data:

Symptom questionnaire data for individual symptoms for Overall Experience (Stomach Cramping, Stomach Bloating and Nausea) will be presented.

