### **3.3. Duration of Study**

Subject participation in this study will last up to 37 days. A screening visit (Visit 1) should be performed within 30 days of the colonoscopy. Subjects meeting all eligibility criteria will be enrolled to receive BLI4700. Subjects will return to the clinic the day of

colonoscopy (Visit 2). Subjects with clinically significant laboratory abnormalities and/or ongoing adverse events related to the study preparation may return for a follow up visit 7 days after colonoscopy.

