#### **4.3. Visit 2**

After completing both preparation doses, subjects will return to the study center for their afternoon colonoscopy. Sites should attempt to schedule subjects a minimum of 4 days from date of screening to allow for receipt and review of screening lab results up to a maximum of 30 days. Visits scheduled beyond 30 days from Visit 1 will be considered a protocol violation and subjects must have a repeat blood draw.

Subjects will bring back their questionnaires and study personnel will review the questionnaires for completeness so that any missed responses can be captured. Subjects will complete a preference questionnaire. Any violations of the dietary restrictions must be confirmed with the subject.

Subject's vital signs will be repeated, a physical examination will be performed, and the subject will be queried for occurrence of adverse events and changes in concomitant medications. Blood samples will be collected for chemistry testing.

The colonoscopy will be performed by a physician according to the site's standard procedures and evaluated on a 4-point scale, as shown in Section 4.6. The colonoscopy procedure will be video recorded through the endoscope at selected research centers.

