## **5. ADVERSE EVENTS**

### **5.1. Adverse Event Definition and Reporting**

An Adverse Event (AE) is any untoward medical occurrence associated with the use of a drug in humans, whether or not considered drug related. An AE can therefore be any unfavorable and unintended sign (including a clinically significant abnormal laboratory finding), symptom, or disease temporally associated with the use of a medicinal (investigational) product. Subjects will be queried for any problems they experienced during and after preparation by site personnel. Symptoms on the symptom scale rated as 2 (mild) to 5 (severely distressing) must be reported as an adverse event. Colonoscopy and biopsy findings are not considered adverse events unless considered by the investigator to be related to the preparation or colonoscopy procedure.

Adverse event collection will commence at the time the patient provides informed consent. Subjects that have an ongoing treatment emergent adverse event or clinically significant abnormal laboratory value will be followed up approximately one week after colonoscopy.

Subjects will be instructed to promptly report adverse events to the Investigator. The Investigator will record date/time of report, date/time of onset, description of the adverse event, severity of adverse event, action(s) taken regarding treatment of the event, action(s) taken regarding study participation, duration of adverse event, and the Investigator's assessment of relationship of adverse event to study preparation.

The Investigator should assess the severity of each adverse event using the following categories:

Grade	Severity	Description
1	Mild	Barely noticeable, does not influence functioning causing no limitations of usual activities
2	Moderate	Makes participant uncomfortable, influences functioning causing some limitations of usual activities
3	Severe	Severe discomfort, treatment needed Severe and undesirable, causing inability to carry out usual Activities
4	Life threatening	Immediate risk of death, Life threatening or disabling (Must be reported as serious adverse event)
5	Fatal	Causes death of the participant (Must be reported as serious adverse event)

The Investigator should assess the relationship to study drug for each adverse event using the following categories:

Categories of Attribution:	Description
UNRELATED	There is no evidence of any causal relationship.

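### The fourth date rule for treatment emergence has no exception for worsening, so it contradicts the definition in the same section

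*Combined protocol and SAP*

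**What the plan says.** Section 9.2 (Study Endpoints - Safety) summarises all AEs by treatment emergence. Its definition has two limbs: a sign or symptom that first appears after the first dose, and one for which "it was present prior to the first dose and subsequently worsened in severity".

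Four date rules follow, introduced by: "In order to define treatment emergence for events with missing start or stop dates the following additional criteria will be used". The first two count an event with a missing onset date as treatment-emergent, either when the resolution date is also missing or when it falls after the first dose. The third does the same for an onset after the first dose. The fourth applies "if the onset date for an event falls before the initiation of the first dose and the stop date is missing or present", and its result is that the event is not treatment-emergent. It has no exception.

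On data capture, Section 5.1 says: "Adverse event collection will commence at the time the patient provides informed consent". It also lists the items for each event: "The Investigator will record date/time of report, date/time of onset, description of the adverse event, severity of adverse event". The list goes on to actions taken, duration and relationship to the preparation. It contains no date of worsening and no instruction to open a new record when severity rises.

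**The concern.** The definition includes pre-dose events that worsen, and the fourth rule excludes every event with a pre-dose onset. A programmer who applies the rule literally drops an event that a programmer who applies the definition keeps, and the plan gives no order of precedence.

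The study has no comparator and its safety summaries are descriptive, so the AE percentages carry much of the safety reading. The case can arise in this population. Section 3.5.1 admits subjects whose indication is abdominal pain, diarrhea or constipation of unknown cause, or inflammatory bowel disease, and Section 5.2 expects abdominal pain, nausea and vomiting from the preparation. Section 5.1 also uses the term treatment-emergent when it says who is followed up about a week after colonoscopy, so the ambiguity reaches beyond the tables.

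**Working it through.** The plan gives no figure to reproduce. The check is to apply both texts to every kind of event with a known onset before Dose 1.

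| Case | Worsened after Dose 1 | Stop date | Definition | Fourth rule | Result |
|---|---|---|---|---|---|
| a | No | Recorded | Not emergent | Not emergent | Agree |
| b | No | Missing | Not emergent | Not emergent | Agree |
| c | Yes | Missing | Emergent | Not emergent | Conflict |
| d | Yes | Recorded | Emergent | Not emergent as worded | Conflict, unless the lead-in removes it |

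Case (d) depends on scope. The lead-in confines the rules to events with a missing date, and on that reading only the definition governs (d). The fourth rule's own condition, however, expressly includes events with a stop date. Case (c), for example an event still ongoing, lies inside the rules on either reading, so the conflict there does not depend on how the lead-in is read.

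**Can such events be on record?** Yes.
- AE collection starts at consent (Section 5.1).
- Section 3.3 says "A screening visit (Visit 1) should be performed within 30 days of the colonoscopy", and Section 4.3 says "Sites should attempt to schedule subjects a minimum of 4 days from date of screening", with a maximum of 30 days. The scheduled gap is therefore 4 to 30 days.
- Dose 1 is taken on the morning of colonoscopy, about 8 hours before it (Sections 4.1.1 and 4.2). Nearly all of the gap is pre-dose.

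**What narrows the exposed group?**
- Conditions ongoing at Visit 1 are recorded as medical history (Section 4.1). The plan does not say which onset date applies if one of them worsens and is reported as an AE.
- A worsening entered as a new event with a post-dose onset is caught by the third rule.
- Ratings for three symptoms are shown separately: "Symptom questionnaire data for individual symptoms for Overall Experience (Stomach Cramping, Stomach Bloating and Nausea) will be presented". That table has no item for vomiting or overall discomfort, both of which Section 5.2 lists as expected.

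**Weight of one affected subject.**
- At the maximum enrolment of 60 (Section 9.3): 1/60 = 0.0167, or 1.7 percentage points.
- Within one formulation, assuming the two in Section 3.4 were split 30/30: 1/30 = 0.0333, or 3.3 percentage points. The plan gives no split.

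**The case against.** The strongest defence is that the two texts fit together if each AE carries one severity. Section 5.1 lists a single severity item, so a symptom that worsens after Dose 1 would become a second event with a post-dose onset. The third rule captures that second event, and the fourth rule correctly leaves the first one as pre-dose. The date rules are also called additional criteria, which suggests that they supplement the definition and do not override it. The data collection forms, which the sponsor supplies (Section 12.4), are not in the documents and may already contain the needed instruction. Finally, Section 5.1 requires symptom-scale ratings of 2 to 5 to be reported as AEs, so cramping, bloating and nausea during preparation are not lost. This is a descriptive pilot, and no safety test or threshold depends on the rule.

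Part of this stands. The conflict has an effect only where a worsened event stays under its original onset date, and the forms might prevent that. The small practical weight is also conceded. The rest does not remove the problem:
- The reading with a second record is an inference that no section states.
- Additional criteria written for missing dates still cover a worsened event with no stop date.
- A symptom reported as an AE because of its rating still falls under the fourth rule if its onset is recorded as pre-dose.

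Section 9.2 also does not say outright that events that are not treatment-emergent are left out of every table, but summarising by treatment emergence has that ordinary meaning.

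**Conclusion.** The concern holds. For a pre-dose event that worsens after Dose 1 and keeps its original onset date, the fourth rule gives a result that contradicts the plan's own definition. This is certain when the stop date is missing, and it also applies to events with a recorded stop date if the rule is taken as worded.

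How many events are affected cannot be computed and may be small or zero. No net bias is claimed in the AE rates, because the first two rules push events with a missing onset date the other way, towards treatment-emergent. The point should be fixed because it lies in the rule behind every AE summary and the correction is simple. The conclusion assumes that the unseen forms do not already require a new record when severity rises. If they do, the wording still needs correcting, but the effect on the counts would largely disappear.

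**What to change.** Amend the fourth rule in Section 9.2 so that an event with onset before the first dose is not treatment-emergent unless its severity increased after the first dose, whether or not a stop date is recorded. Have the AE form capture that increase, for example as a new record with its own onset date and time, and say so in Section 5.1.

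The cost is one clause in the analysis section and one form-completion instruction. Dosing, visits and sample size are unchanged. The reported AE rate may look slightly less favourable.

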### **9.3. Sample Size**

Up to 60 subjects may be enrolled and treated in the study. This size was chosen because of the pilot nature of this study.

## **10. DRUG INVENTORY AND DISPOSITION**

At the conclusion of the study, all drug materials will be accounted for. Federal law requires that, at the conclusion of the study, all drug materials must be returned to the study sponsor or destroyed according to local regulations.

## **11. STUDY MONITORING**

A Braintree Laboratories Study Monitor or qualified designee will visit each study center prior to the commencement of the study and periodically during the course of the study in accordance with federal guidelines governing the sponsorship of studies.

## **12. DOCUMENTS AND NOTIFICATIONS**

### **12.1. Informed Consent**

Written informed consent will be obtained from the subjects by study personnel and will be kept on file at the study center. Documentation of the consent process should be noted in the study source documents.

### **12.2. Institutional Review Board**

Peer review and approval of the protocol by an appropriate Institutional Review Board is required prior to commencement of enrollment. Amendments to the approved protocol must also be submitted to the Institutional Review Board and approved prior to their implementation.

### **12.3. Amendments to the Protocol**

If Braintree Laboratories determines that there is need for an amendment, it will be produced in writing by Braintree Laboratories and will be made a formal part of the protocol following its submission and approval from the IRB.

### **12.4. Data Records**

Braintree Laboratories will provide data collection forms for each subject. Subject medical records will be reviewed to verify all other data points, including potential adverse events. Copies of subjects' laboratory reports, colonoscopy and pathology

reports (if applicable) will be collected for Braintree Laboratories after subject identifiers have been redacted by site staff. Colonoscopies at selected research centers will be recorded and transmitted to Braintree Laboratories. The Investigator should retain copies of the subject consent forms and other study documents for a period of two years following the date of approval of a New Drug Application or supplement for BLI4700, or, if the application is not approved, for two years after the drug investigation program is discontinued. The study investigator will notify Braintree Laboratories of their intent to dispose of the study records and allow Braintree to take possession of such records. Study records will be made available at reasonable times for inspection and copying if requested by a properly authorized employee of Braintree Laboratories, authorized Braintree Laboratories designee or the Department of Health and Human Services in accordance with federal regulations.

### **13. PUBLICATION AND AGREEMENT**

The results of this study will be published if mutually agreed by Braintree Laboratories and the Investigator and at a mutually agreed upon date. Investigator agrees to submit to Braintree Laboratories, within sixty (60) days of the proposed submission date, any proposed publication or presentation for prior review. Braintree Laboratories will, within thirty (30) days after receipt, advise if there is any proprietary or patentable information, which should not be disclosed at the present time. Investigator shall not release any such proposed publication or presentation, if so notified by Braintree Laboratories.

**APPENDIX A: PREPARATION INSTRUCTIONS**

**APPENDIX B: PATIENT QUESTIONNAIRES**
